### L-Menthol Injection as a Novel Technique during Colonoscopy: The MINT-C study

#### **Primary Objectives:**

1. Evaluate for changes in adenoma detection rates with the use of intraluminal peppermint oil application vs sterile water application during colonoscopy.

#### Secondary Objectives (non co-primary; non-key secondary end points):

1. Evaluate for changes in Polyp detection rates

2. Evaluate for changes in total procedure time, cecal intubation time, and withdrawal time with the use of intraluminal peppermint oil application vs placebo during colonoscopy.

3. Evaluate for changes in advanced adenoma detection rates with the use of intraluminal peppermint oil application vs placebo during colonoscopy. Advanced adenoma will be defined as an adenoma with significant villous features (>25%), size of 1.0 cm or more, high-grade dysplasia, or early invasive cancer.

4. Evaluate for changes in cancer detection rates with the use of intraluminal peppermint oil application vs placebo during colonoscopy.

5. Evaluate for changes in reported patient comfort levels with the use of intraluminal peppermint oil application vs placebo during colonoscopy.

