#### Solution B) Placebo solution

Ingredients:

- 1) 0.4mL of Tween® 80 (i.e. Polysorbate 80) this is a commonly used food additive that acts as a surfactant to bring the peppermint oil into solution
- 2) 1L prepackage sterile water
- 3) 2.6mL of undyed simethicone

Instructions to prepare:

- 4) Add tween and simethicone to sterile water. Then, shake vigorously.
- 5) Once solution has settled, and patient has been randomized, draw 20mL of solution into a plastic syringe

In the morning of the procedure, patients undergoing screening and surveillance colonoscopy will be pre-screened to evaluate if they meet inclusion criteria. Once patients are identified they will be approached by study personnel (consisting of PI, co-investigators, and additional staff supervised by the PI or co-investigators) to determine their willingness to participate in the study. If the subject is willing to participated, he or she will undergo written consent for participation in the study by research protocol personnel. Patients will be questioned regarding their allergy status specific to peppermint oil and this will be documented in the consent form and in the REDCap database.

Once the patient is willing to participate and inclusion/exclusion criteria are met based on prescreening in the EMR, which includes evaluation of prior baseline labs, designated research personnel (that will not be involved in the actual colonoscopy) will draw up 20mL of solution in each of 4 total plastic syringes. Placebo and experimental solutions will be similar in appearance. These syringes will be placed on the endoscopy cart to be used by the endoscopist during the procedure as described in the paragraphs below.

Endoscopy rooms being used for this study will use an essential oil diffuser to add olfactory blidning. As the experimental solution has a distinct odor of peppermint oil, the diffusing device will prevent olfactory detection by the endoscopist and staff.

Endoscopists and trainees working with supervising endoscopists will be provided with a total of four (4) 20mL prefilled syringes consisting of either solution A (1.6% peppermint oil, which is 0.8% L-menthol) or solution B (protocol). Both solutions are similar in appearance.

Endoscopists will be required to deliver 1 syringe at the cecum and 1 syringe in the sigmoid colon. Up to 2 additional doses can be delivered at the discretion of the endoscopist up to a maximum of 4 total doses (**max total dose = 640mg L-Menthol**).

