After the procedure, endoscopists will be provided with a survey which will ask them to identify in which arm of the trial they participated. Additionally patients will be provided a survey at the end of the procedure to rate their pain and discomfort during the procedure. Both surveys are available for review at the end of this protocol.

ADR, PDR, total procedure time, cecal intubation time, withdrawal time, advanced adenoma detection rates, and cancer detection rates will be calculated and compared between both groups. Statistical analysis methods are described below.

Patients will be followed up by telephone as described in the section below titled, "Follow up after completion of procedure".

**Type of Blinding**: Fully masked through the use of identical appearing solutions and additional measures to maintain blinding, such as using an essential oil diffuser to create a peppermint oil smell in the room to prevent olfactory detection of peppermint oil. In addition, effectiveness of

blinding will be assessed by providing the endoscopist with a survey asking him or her to guess which group to which their patient belonged. Also, blinded adjudication of key outcomes, such as adverse events leading to premature discontinuation of the procedure will be carried out.

**Allocation concealment:** serially numbered, opaque, sealed envelopes; variable block randomization

**Sample Size (Including Ratio of Subjects Assigned to Treatments)/Power:** This study is projected to enroll a total of 300 subjects (150:150) in group 1 and 2 respectively. Given a power of 80% and a confident level of 95% with a p-value of 0.05, to determine a 20% difference in ADR between both groups, a sample size of 274 is required. Accounting for poor preps or withdrawal of consent, an increase in the sample size to 300 is projected.

**Randomization:** Subjects will be randomized in the two treatment arms in a 1:1 ratio. Randomization will be based on a computer-generated random code schedule and will occur immediately prior to beginning the procedure so as to keep drop out rate to a minimum.

**Stratification:** Eligible patients will stratified into 2 groups, those undergoing primary screening colonoscopies and those undergoing surveillance colonoscopies. They will also be stratified by institution.

**Diagnosis and Criteria for Inclusion:** Adult subjects who are undergoing screening or surveillance colonoscopies.

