#### **Exclusion Criteria:**

- 1. History of colectomy, partial or complete
- 2. Symptoms suggesting possible colorectal stenosis or cancer
- 3. Inflammatory bowel disease
- 4. Familial polyposis syndromes
- 5. History of, or current diagnosis of colorectal cancer
- 6. American Society of Anesthesia Physical Stats (ASA PS) score of IV or greater
- 7. Non-correctable coagulopathy
- 8. Currently receiving anti-thrombotic therapy, with an INR > 1.5
- 9. Poor prep, total BBPS score < 6, or any part of the colon < 2.
- 10. Patients with known allergy to peppermint oil or peppermint containing products.

11. Patients taking calcium channel blockers (Amlodipine, Nifedipine, Verapamil, Diltiazem, Dihydropyridine, Felodipine, etc).

**Product, Dose, Mode of Administration**: Peppermint oil solution will be prepared as described above in 20mL aliquots of 1.6% peppermint oil. A total of 4 separate 20mL aliquots will be provided in standard plastic syringes for patient who are randomized to the experimental arm of the trial. The placebo solution will be provided in the same fashion in 4 separate 20mL aliquots provided to those randomized to the placebo arm of the trial. The endoscopist will be required to inject the contents of the provided syringes through the endoscope at specific times during the procedure. The first dose will be delivered during the withdrawal portion of the exam in the cecum. After this the endoscopist should proceed with the exam as per standard procedure. A second dose will be delivered in proximal portion of the sigmoid colon. Up to two additional doses can be delivered at any time during the procedure as per the judgment of the endoscopist. Importantly, after injecting the 20mL of solution through the endoscope, the physician will also inject an additional 20mL air through the endoscope to ensure the complete dose was delivered. The endoscopists will note where all doses were delivered in the post procedure survey.

The dosing below and the protocol above has been approved by the FDA IND committee:

Each 20mL aliquot of experimental solution contains: 160mg L-Menthol (320mg Peppermint oil) The maximum delivered dose is 4 separate 20mL aliquots: 640mg L-menthol (1280mg peppermint oil).

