#### **Criteria for Evaluation:**

Safety assessments will be conducted at start and finish of colonoscopy. Patients will have blood tests reviewed in the electronic medical records system and undergo standard pre-endoscopy history and physical examinations. ADRs will be calculated after colonoscopies are completed. Total time spent in colonoscopy including withdrawal time (defined as time taken to withdraw endoscope from cecum to the end of the patient's GI tract) will be recorded. The bowel-prep will be graded according to Boston bowel prep score (BPPS) and recorded for each patient.

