#### Data Analysis Plan:

Descriptive statistics will be used for ADRs, total procedure time, withdrawal time, bowel prep scoring, and pain severity during procedure. The primary and secondary endpoints will be determined on an intention-to-treat basis. ADRs will be calculated based on results from pathology. Differences in ADR will be analyzed using chi-square test. No interim analyses will be performed. Resource use will be prospectively recorded in a disaggregated form.

This study is projected to enroll a total of 300 subjects (150:150) in group 1 and 2 respectively. Given a power of 80% and a confident level of 95% with a p-value of 0.05, to determine a 20% difference in ADR between both groups, a sample size of 274 is required.

Based on our internal review of our institutions experience with patients with poor preps and the very low Accounting for poor preps or withdrawal of consent, an increase in the sample size to 300 is projected. We estimate that approximately 1000 patients will be screened for participation in this study to accommodate for patients that are not interested or not candidates for the study.

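### On the stated dosing order, cecal intubation time ends before any study solution is given, so it cannot be read as an effect of peppermint oil

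*Combined protocol and SAP*

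**What the plan says.** Item 2 of the Secondary Objectives is to "Evaluate for changes in total procedure time, cecal intubation time, and withdrawal time" with peppermint oil against placebo. The section heading marks these endpoints as neither co-primary nor key secondary. The Methodology text that follows the placebo recipe repeats the plan: "ADR, PDR, total procedure time, cecal intubation time, withdrawal time, advanced adenoma detection rates, and cancer detection rates will be calculated and compared" between the two groups.

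Dose timing is given in two places.

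- The paragraph on product, dose and mode of administration (after the Exclusion Criteria) says "The first dose will be delivered during the withdrawal portion of the exam in the cecum". The examination then continues, a second dose goes into the proximal sigmoid, and "Up to two additional doses can be delivered at any time during the procedure as per the judgment of the endoscopist".
- The Methodology text requires one syringe at the cecum and one in the sigmoid, without naming insertion or withdrawal. It adds "Up to 2 additional doses can be delivered at the discretion of the endoscopist", with no timing.

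Three further statements bear on the point. Randomization "will occur immediately prior to beginning the procedure". The Criteria for Evaluation section gives "withdrawal time (defined as time taken to withdraw endoscope from cecum" as the start of its definition. The Data Analysis Plan states: "The primary and secondary endpoints will be determined on an intention-to-treat basis".

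**The concern.** An outcome can show a treatment effect only if it is still open when treatment starts. Cecal intubation time is not defined in the documents. In its ordinary sense it runs from insertion until the cecum is reached, which fits a withdrawal time that starts at the cecum. If the first dose is given there, during withdrawal, the clock on cecal intubation has already stopped.

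The objective nevertheless presents the variable as something that may change with peppermint oil, and no section labels it a balance check. A chance difference could then be reported as the oil speeding or slowing insertion, and a null result as evidence that it does not. Neither statement would be supported.

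**Working it through.** The plan gives no figure for this endpoint, so there is none to reproduce. The main check is the order of events.

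**Order of events**

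1. Randomization, immediately before the procedure (Randomization paragraph).
2. Insertion up to the cecum. Cecal intubation time ends here.
3. Withdrawal starts at the cecum (Criteria for Evaluation).
4. First dose, in the cecum during withdrawal (dosing paragraph).
5. Second dose, proximal sigmoid (dosing paragraph).

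Step 2 falls after randomization but before any dose. The expected drug effect on it is 0. A test at a two-sided 0.05 level would be significant 5% of the time at any sample size, as for any outcome with no effect.

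**What could still produce a difference**

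Chance, faulty allocation and loss of masking are possible. So is loss of patients after randomization. Poor preparation is an exclusion criterion, defined by a Boston score below 6 in total or below 2 in any part of the colon, and segment scores are available only once the colon is examined. The sample size is raised from 274 to 300 for poor preparation or withdrawn consent, an allowance of 26/300 = 8.7%. If such patients leave the analysis unequally by arm, cecal intubation time can become unbalanced without any drug effect.

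**If an optional dose may precede the cecum**

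This is an illustration. Only the 150 per arm comes from the documents. Assumed: a two-sided comparison of two means at 0.05 (no test is named for the times), a common SD, and an equal share f of each arm given a dose before the cecum. The documents give no f, so a range is shown.

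- Intention-to-treat difference: δ = f × effect in those dosed early.
- Standard error in SD units: √(2/150) = 0.1155.
- Smallest difference with 80% power: (1.960 + 0.842) × 0.1155 = 0.32 SD.
- Effect needed in those dosed early: 0.32/f.
- Power: Φ(δ/0.1155 − 1.960) + Φ(−δ/0.1155 − 1.960).

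| f (assumed) | Effect needed in those dosed early, for 80% power | δ if that effect is 0.5 SD (assumed) | Power |
|---|---|---|---|
| 10% | 3.2 SD | 0.05 SD | 7% |
| 25% | 1.3 SD | 0.125 SD | 19% |
| 50% | 0.65 SD | 0.25 SD | 58% |

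With an assumed effect of 0.3 SD in those dosed early, power is about 6%, 10% and 26%.

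**The case against.** The strongest reply is that the dosing paragraph is already in sequence. It names a first dose, says what follows it, names a second and then speaks of additional ones, so the optional doses naturally come after the cecal dose. That is the better reading, and it strengthens the main point, because on it cecal intubation time is wholly pre-dose. A reader might infer that the protocol contradicts itself outright on dosing. The text does not support that: one phrase is loose, and the Methodology section gives no timing that could conflict. The looseness still matters, because read literally it would allow a dose during insertion.

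A second reply is that the plan commits to no test and no causal reading for this variable. The Data Analysis Plan names a chi-square test for ADR only, and its list for descriptive statistics omits cecal intubation time. That is so, and the harm depends on how the result is later read. But the objective is worded as a change with the use of peppermint oil, which invites that reading.

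Third, endoscopists are to note where each dose was delivered, which might show whether any was given early. The survey form is not in the text available here, so it cannot be said that this information will be missing. A location alone may not separate insertion from withdrawal, and a record made afterwards does not replace a stated rule.

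Finally, the power table rests on assumed inputs and on the less natural reading. It shows how dilution works and does not measure an error in this protocol.

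**Conclusion.** The point holds. On the stated order, the part of secondary objective 2 that concerns cecal intubation time cannot be answered: the expected drug effect is zero, and neither a difference nor its absence is evidence about peppermint oil. This rests on the ordinary meaning of cecal intubation time and on the first dose being given in the cecum during withdrawal. If doses may come earlier, the outcome can carry an effect, but only through the patients so dosed and diluted by their share.

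Three stronger conclusions might be drawn and are not supported.

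- A difference would not have to mean chance, faulty allocation or loss of masking. Exclusion after randomization is another route.
- The other time outcomes are not undermined. Withdrawal time starts at the cecum, and total procedure time includes withdrawal. Nothing in the documents calls for ranking the time outcomes or for barring adjustment of total procedure time.
- The primary result is not touched. The ADR analysis does not use this variable.

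Severity is minor.

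**What to change.** Reconcile the sentence that places the first dose with the sentence on optional doses, both in the dosing paragraph, and align the Methodology text with the result. This review does not say which timing is right. Settle the role of cecal intubation time from that text before the data are seen.

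- **If no dose can precede the cecal dose:** take cecal intubation time out of the treatment-effect outcomes in secondary objective 2 and in the Methodology list. Suggested wording: *Because no dose is given before the cecal dose, cecal intubation time will be reported by arm as a pre-dose balance check and will not be interpreted as an effect of peppermint oil.*
- **If doses may precede the cecum:** keep the outcome and add: *Any effect on cecal intubation time can arise only in patients dosed before the cecum was reached and is diluted under intention-to-treat.*

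The cost is one clarifying sentence on dose timing and a relabelling in two places. No extra patients, data or procedures are needed.

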#### Methodology:

The institutional investigational pharmacy at each site will create and dispense a 1 liter solution containing 1.6% peppermint oil (solution A) or placebo (solution B). Once a patient consents for the procedure and is brought to the endoscopy room, research personel will selecte an opaque envelope that is serially numbered, labeled, and randomly assigned in a variable block fashion with a 1:1 ratio in blocks of 4 or 6 stratified by institution and indication for procedure (surveillance or screening). This contents of envelope will contain a paper assigning the patient to the either solution A or solution B. The research personal will draw up 20mL of this solution in each of 4 total plastic syringes. These syringes will be placed on the endoscopy cart to be used by the endoscopist during the procedure as described in the paragraphs below. Each site will also utilize an essential oil diffusing device in the endoscopy suite to mask any smells that could potentially confound blinding.

Solution A) Peppermint oil solution (1.6% peppermint oil, which is 0.8% L-menthol)

Ingredients:

- 1) 16mL of peppermint oil (provided by the NowFoods® company)
- 2) 0.4mL of Tween® 80 (i.e. Polysorbate 80) this is a commonly used food additive that acts as a surfactant to bring the peppermint oil into solution
- 3) 1L prepackage sterile water
- 4) 2.6mL of undyed simethicone

Instructions to prepare:

- 1) Add peppermint oil, tween, and simethicone to sterile water. Then, shake vigorously.
- Once solution has settled, and patient has been randomized, draw 20mL of solution into a plastic syringe
- 3) As a result, in our each syringe will contain **160mg of L-Menthol.**

#### Solution B) Placebo solution

Ingredients:

- 1) 0.4mL of Tween® 80 (i.e. Polysorbate 80) this is a commonly used food additive that acts as a surfactant to bring the peppermint oil into solution
- 2) 1L prepackage sterile water
- 3) 2.6mL of undyed simethicone

Instructions to prepare:

- 4) Add tween and simethicone to sterile water. Then, shake vigorously.
- 5) Once solution has settled, and patient has been randomized, draw 20mL of solution into a plastic syringe

In the morning of the procedure, patients undergoing screening and surveillance colonoscopy will be pre-screened to evaluate if they meet inclusion criteria. Once patients are identified they will be approached by study personnel (consisting of PI, co-investigators, and additional staff supervised by the PI or co-investigators) to determine their willingness to participate in the study. If the subject is willing to participated, he or she will undergo written consent for participation in the study by research protocol personnel. Patients will be questioned regarding their allergy status specific to peppermint oil and this will be documented in the consent form and in the REDCap database.

Once the patient is willing to participate and inclusion/exclusion criteria are met based on prescreening in the EMR, which includes evaluation of prior baseline labs, designated research personnel (that will not be involved in the actual colonoscopy) will draw up 20mL of solution in each of 4 total plastic syringes. Placebo and experimental solutions will be similar in appearance. These syringes will be placed on the endoscopy cart to be used by the endoscopist during the procedure as described in the paragraphs below.

Endoscopy rooms being used for this study will use an essential oil diffuser to add olfactory blidning. As the experimental solution has a distinct odor of peppermint oil, the diffusing device will prevent olfactory detection by the endoscopist and staff.

Endoscopists and trainees working with supervising endoscopists will be provided with a total of four (4) 20mL prefilled syringes consisting of either solution A (1.6% peppermint oil, which is 0.8% L-menthol) or solution B (protocol). Both solutions are similar in appearance.

Endoscopists will be required to deliver 1 syringe at the cecum and 1 syringe in the sigmoid colon. Up to 2 additional doses can be delivered at the discretion of the endoscopist up to a maximum of 4 total doses (**max total dose = 640mg L-Menthol**).

After the procedure, endoscopists will be provided with a survey which will ask them to identify in which arm of the trial they participated. Additionally patients will be provided a survey at the end of the procedure to rate their pain and discomfort during the procedure. Both surveys are available for review at the end of this protocol.

ADR, PDR, total procedure time, cecal intubation time, withdrawal time, advanced adenoma detection rates, and cancer detection rates will be calculated and compared between both groups. Statistical analysis methods are described below.

Patients will be followed up by telephone as described in the section below titled, "Follow up after completion of procedure".

**Type of Blinding**: Fully masked through the use of identical appearing solutions and additional measures to maintain blinding, such as using an essential oil diffuser to create a peppermint oil smell in the room to prevent olfactory detection of peppermint oil. In addition, effectiveness of

blinding will be assessed by providing the endoscopist with a survey asking him or her to guess which group to which their patient belonged. Also, blinded adjudication of key outcomes, such as adverse events leading to premature discontinuation of the procedure will be carried out.

**Allocation concealment:** serially numbered, opaque, sealed envelopes; variable block randomization

**Sample Size (Including Ratio of Subjects Assigned to Treatments)/Power:** This study is projected to enroll a total of 300 subjects (150:150) in group 1 and 2 respectively. Given a power of 80% and a confident level of 95% with a p-value of 0.05, to determine a 20% difference in ADR between both groups, a sample size of 274 is required. Accounting for poor preps or withdrawal of consent, an increase in the sample size to 300 is projected.

**Randomization:** Subjects will be randomized in the two treatment arms in a 1:1 ratio. Randomization will be based on a computer-generated random code schedule and will occur immediately prior to beginning the procedure so as to keep drop out rate to a minimum.

**Stratification:** Eligible patients will stratified into 2 groups, those undergoing primary screening colonoscopies and those undergoing surveillance colonoscopies. They will also be stratified by institution.

**Diagnosis and Criteria for Inclusion:** Adult subjects who are undergoing screening or surveillance colonoscopies.

**Facilities Description and Patient Population:** This study will be carried out in two separate facilities in order to capture a broad patient population base with various rates of baseline ADRs. The first is a large-tertiary referral care center that performs over 5000 diagnostic and screening colonoscopies per year. The second institution is a large Veterans Affairs Medical Center that also performs over 3500 colonoscopies per year.

The subject must meet ALL criteria listed below for entry:

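### The 274 patients stated for 80% power and a 20% ADR difference cannot be reproduced as 20 percentage points at any control ADR; neither the control ADR nor the scale is given

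*Combined protocol and SAP*

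**What the plan says.** The sample-size statement appears twice, under the Sample Size/Power item of the Methodology section and again in the Data Analysis Plan. Both read "Given a power of 80% and a confident level of 95% with a p-value of 0.05", and then "to determine a 20% difference in ADR between both groups, a sample size of 274 is required". Allocation is 1:1. The 274 is a total, because losses are then added to reach 300, split 150:150: "Accounting for poor preps or withdrawal of consent, an increase in the sample size to 300 is projected".

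The Data Analysis Plan fixes the test ("Differences in ADR will be analyzed using chi-square test") and rules out interim looks ("No interim analyses will be performed"). ADR is the only primary objective.

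No section gives an expected ADR in either arm, the scale of the 20%, the sidedness of the test or the formula. The only remark on the control rate is in Facilities Description and Patient Population, where two sites are used "in order to capture a broad patient population base with various rates of baseline ADRs".

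**The concern.** A sample size for two proportions depends on the control rate as well as on the difference, so a total quoted without a control rate cannot normally be checked. Here it can be checked in part. For a fixed absolute difference the required number has a ceiling over all control rates, and 274 lies well above that ceiling for 20 percentage points at 80% power.

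The enrolment of 300 is derived from this sentence, and the sentence is the only statement of what ADR effect the trial was sized to find. If the trial shows no difference, readers will ask what difference it could have detected. As written, the answer is wrong on the absolute reading and unsupported on the relative one.

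**Working it through.** **Inputs.** From the plan: power 80%, alpha 0.05, 1:1 allocation, chi-square test, a difference of 20%, total 274 (137 per arm). Not in the plan, so scanned or assumed: control ADR, scale, sidedness.

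**Formula.** Pooled-variance comparison of two proportions, with p̄ = (p₁ + p₂)/2 and d = |p₂ − p₁|:

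n per arm = [z(α)·√(2p̄(1−p̄)) + z(β)·√(p₁(1−p₁) + p₂(1−p₂))]² / d²

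where z(α) = 1.960 (two-sided) and z(β) = 0.842. The continuity-corrected size is n′ = (n/4)·[1 + √(1 + 4/(n·d))]². Totals are twice the per-arm number rounded up.

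**Step 1: try to reproduce 274 as 20 percentage points.** The variance is greatest when the two rates straddle 50%, so the worst case is 40% against 60%:

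- n = (1.960 × 0.7071 + 0.842 × 0.6928)² / 0.20² = (1.3859 + 0.5831)² / 0.04 = 96.9, so 97 per arm and **194** in total.
- With continuity correction: (96.92/4) × [1 + √(1 + 4/19.38)]² = 106.7, so 107 per arm and **214** in total.

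Scanning the control ADR in 0.1-point steps confirms these as maxima:

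| Method (20 points, 80% power) | Largest total at any control ADR |
|---|---|
| Two-sided, pooled | 194 |
| Two-sided, continuity-corrected | 214 |
| Two-sided, unpooled | 190 |
| Two-sided, arcsine | 194 |
| One-sided, pooled | 154 |
| One-sided, continuity-corrected | 172 |

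Fisher's exact test, checked at 40% against 60% only, needs about 216 (108 per arm gives 80.2% power). None of these approaches 274.

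**Step 2: what 274 delivers on the absolute reading.** Power = Φ{[d√n − z(α)√(2p̄(1−p̄))] / √(p₁(1−p₁) + p₂(1−p₂))}. At 40% against 60% with n = 137: (0.20 × 11.705 − 1.3859)/0.6928 = 1.378, which is **91.6%**. This is the minimum over all control ADRs (89.5% with correction). With 150 per arm the minimum is 93.8% (92.2% with correction).

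Solving instead for the difference detectable with 80% power (two-sided, no correction), at assumed control ADRs:

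| Control ADR | 274 patients | 300 patients |
|---|---|---|
| 20% | 15.1 points | 14.3 points |
| 30% | 16.4 | 15.6 |
| 40% | 16.8 | 16.1 |
| 50% | 16.6 | 15.9 |
| 60% | 15.7 | 15.1 |

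The largest value for 274 patients at any control ADR is 16.9 points (about 17.6 with correction).

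**Step 3: try to reproduce 274 as a relative 20% increase.** At 70.5% against 84.6%: p̄ = 0.7755 and d = 0.141, so n = (1.960 × 0.5901 + 0.842 × 0.5816)² / 0.141² = 136.3. That is 137 per arm and **274** in total. With continuity correction the match moves to a control ADR of 72.1%. One-sided, it falls at 66.5% (68.4% with correction). At lower assumed control ADRs, two-sided without correction:

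| Control ADR | Total needed for 80% | Power with 274 |
|---|---|---|
| 30% | 1,926 | 18% |
| 40% | 1,208 | 26.5% |
| 50% | 776 | 38% |
| 60% | 488 | 55.5% |
| 70% | 282 | 79% |

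**Step 4: other explanations.**

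- Losses do not account for 274. The allowance is added afterwards and amounts to 1 − 274/300 = 8.7%. Getting from 194 to 274 would need a second, unstated allowance of 1 − 194/274 = 29%.
- No interim looks or co-primary endpoints call for inflation.
- For 20 points, 90% power without correction peaks at 260. With correction it gives exactly 274 at control ADRs of 32.4–33.7% and 46.3–47.6%, but that contradicts the stated 80%.

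**The case against.** The strongest reply is that the arithmetic error is proven only if the 20% means percentage points. The plan is silent on scale, and on the relative reading 274 is exactly right at a control ADR of 70.5%. What is proven without conditions is that an input is missing. This stands. The claim that 274 exceeds every possible requirement, and the word conservative, belong to the absolute reading only. On the relative reading with a control ADR below about 70%, the direction reverses.

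A second reply is that the absolute reading is harmless, since the trial then does more than it promises and nothing in its conduct changes. That is also fair, and it limits the weight of the mismatch itself. It does not dispose of the point, because the plan does not establish the absolute reading: the same sentence is compatible with power above 91% and with power below 40%.

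Two cautions apply to the evidence. The powers in the relative table rest on control ADRs assumed for this review and say nothing about the sites' actual rates. The match at 90% power with continuity correction is one of several input sets that can land near 274 (alpha of 0.01 is another), so it is a line of enquiry for the sponsor and not an explanation.

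**Conclusion.** The concern holds. As 20 percentage points with 80% power at 0.05, 274 cannot be obtained at any control ADR by any of the standard methods tried. The two-sided ceiling is 194, or 214 with continuity correction, so 274 exceeds the corrected ceiling by 28% (274/214 = 1.28). Either the stated power is too low (it is at least 91.6%) or the stated difference is too large (80% power corresponds to at most 16.9 points without correction).

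As a relative 20% increase, 274 requires a control ADR of about 70–72% two-sided, or 66–68% one-sided. The plan gives no such rate.

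The absolute-reading results need no assumption about the control ADR. The power and minimum-difference figures assume a two-sided test, while the sample-size ceilings were also checked one-sided. This should be fixed. It does not show that the trial is underpowered, but the plan as written does not let a reader rule that out.

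**What to change.** In both the Sample Size/Power item and the Data Analysis Plan:

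1. Recover the inputs behind 274 and state them: the assumed control ADR with its source, whether the 20% is absolute or relative, the sidedness, and the formula including any continuity correction. It is worth checking whether 90% power with continuity correction was used.
2. Recompute from those inputs, and restate the power or the detectable difference so that it agrees with 274.

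On the absolute reading the sentence could run as follows, with 40% as a placeholder for the sponsor's own figure: *A total of 274 patients gives about 92% power for a difference of 20 percentage points, or 80% power for about 17 points, at an assumed control ADR of 40% (two-sided 0.05, chi-square without continuity correction).* If a relative increase was meant, give the power at the assumed control ADR instead.

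The cost is one sentence in each of two places. The restatement adds no patients and does not alter the primary test. The downside is that, if a relative 20% was intended and the control ADR is below about 70%, the honest power figure will be under 80%.
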